APPENDIX VIII: COGNITIVE INTERVIEW SCRIPT – SPANISH

Introducción (léale al participante)

Es importante entender las experiencias de las personas diagnosticadas con HSIL anal (lesiones precancerosas en el ano) (y cualquier tratamiento que reciban – SI APLICA). Por eso le estamos pidiendo ayuda hoy. Nos gustaría que conteste algunas preguntas durante la próxima hora. Le pediremos que conteste algunas de las preguntas nuevas que estamos desarrollando y que luego nos cuente sus experiencias contestando estas preguntas, como por ejemplo, qué tan fácil o difícil fue contestarlas. Algunas preguntas tendrán que ver con los síntomas relacionados con HSIL anal (y tratamiento – SI APLICA). Otras tendrán que ver con la manera en que HSIL anal (y tratamiento – SI APLICA) ha impactado aspectos de su vida diaria. Usted nos ayudará a entender mejor lo que experimentan las personas con HSIL anal. La información que nos de hoy se utilizará en investigación, y ayudará a otras personas en el futuro.

ÍNDICE DE SÍNTOMAS RELACIONADOS CON LA SALUD ANCHOR

A continuación presentamos una lista de afirmaciones que otras personas diagnosticadas con HSIL (lesión precancerosa en el ano) y que han sido tratadas o monitoreadas activamente han dicho que son importantes. Por favor seleccione la casilla con su respuesta basándose en sus experiencias en **los últimos 7 días**.

Si tiene **ALGÚN** problema seleccionando una respuesta o le cuesta contestar algo, por favor seleccione la casilla en la columna que dice, *Difícil de entender*. Déjeme saber cuando haya terminado cada una de estas secciones (Síntomas físicos, Impactos físicos, Síntomas psicológicos).

SÍNTOMAS FÍSICOS	Escoja si no aplica	Para nada 0	Un poco 1	Algo 2	Bastante 3	Muchísimo 4	Difícil de entender
1. Tengo dolor anal							
2. Tengo dolor pero no en el área anal							
3. Tengo dolor cuando entro al baño a defecar							
4. Tengo estreñimiento							
5. Tengo sangrado del ano							
6. Tengo picazón en el ano o alrededor del ano							
7. Tengo una secreción (mojado) en el área anal							
8. Tengo sensación de ardor en el área anal							
9. Siento urgencia de entrar al baño a defecar							
IMPACTOS FÍSICOS	Escoja si no aplica	Para nada 0	Un poco 1	Algo 2	Bastante 3	Muchísimo 4	Difícil de entender
10. Tengo problemas con mi capacidad física para movilizarme							
11. Tengo problemas para sentarme							
12. Tengo problemas terminando las tareas de la casa (por ej., limpiar, cocinar, hacer la colada, llevar la casa)							

13. Tengo problemas con mi arreglo personal diario (por ej., bañándome, vistiéndome, afeitándome)							
14. Tengo problemas participando en actividades de ocio (por ej., mirar televisión, relajarme)							
15. Tengo problemas participando en actividades sociales (por ej., salir a comer, visitar amigos)							
16. Tengo problemas siendo productivo en el trabajo							
SÍNTOMAS PSICOLÓGICOS	Escoja si no aplica	Para nada 0	Un poco 1	Algo 2	Bastante 3	Muchísimo 4	Difícil de entender
17. Tengo dificultad concentrándome							
18. Me ha disminuido el placer de la actividad sexual anal							
19. Me ha disminuido el placer de cualquier forma de actividad sexual diferente a la actividad sexual anal							
20. Me ha disminuido el deseo por la actividad sexual anal							
21. Me ha disminuido el deseo por formas de actividad sexual diferentes a la actividad sexual anal							
22. Me preocupa que mi enfermedad empeore							
23. Tengo ansiedad							
24. Tengo depresión							
25. Tengo problemas con mis relaciones íntimas							

Ahora nos va a contar cuáles fueron sus respuestas para cada una de las 25 preguntas (REGISTRE LAS RESPUESTAS EN SU FORMULARIO). Por favor cuénteme si escogió “Difícil de entender” o “No aplica”.

Sondeo de la entrevista cognitiva – General

Primero, para las cosas que contestó, fue fácil de contestar....

- Todo el tiempo
- La mayoría del tiempo
- Algunas veces
- Nunca

¿Hubo algún problema que hizo difícil contestar la encuesta en general? Si sí, ¿qué?

Ahora examinemos lo que le pareció difícil de entender. Olvidándose de las cosas que ya me ha contado, ¿cuáles fueron los problemas que surgieron en esos momentos?

(Algunos de los asuntos planteados durante esta porción podrían hacer resaltar problemas específicos que forman parte de nuestro objetivo. Por favor tome nota de ellos para que no vuelvan a surgir durante la entrevista).

Sondeo de la entrevista cognitiva – Instrucciones

¿Tuvo algún problema entendiendo las instrucciones? Si sí, por favor describa estos problemas.

*A continuación presentamos una lista de afirmaciones que otras personas diagnosticadas con HSIL (lesión precancerosa en el ano) y que han sido tratadas o monitoreadas activamente han dicho que son importantes. Por favor seleccione la casilla con su respuesta basándose en sus experiencias **en los últimos 7 días**.*

¿Qué significa para usted la palabra “experiencias” tal como se utiliza en estas instrucciones?
¿Preferiría que utilicemos alguna otra palabra o frase?

Sondeo de la entrevista cognitiva – Preguntas específicas

Le preguntaron sobre DOLOR como un síntoma posible relacionado con HSIL anal.

¿Experimenta DOLOR no vinculado con el DOLOR ANAL o DOLOR DURANTE LA DEFECACIÓN?

Si respondió que sí, ¿el DOLOR que usted siente es diferente al DOLOR ANAL o DOLOR DURANTE LA DEFECACIÓN? ¿Le parece que debemos preguntar sobre los tres tipos de DOLOR?

¿Qué quiere decir para usted PICAZÓN EN EL ANO O ALREDEDOR DEL ANO según se preguntó en esta afirmación? ¿Piensa que PICAZÓN EN y PICAZÓN ALREDEDOR deberían ser dos afirmaciones separadas?

Si el paciente experimenta SECRECIÓN (MOJADO):

¿Cuál palabra SECRECIÓN (MOJADO) prefiere para describir esta experiencia? ¿Existe otra palabra o frase que piensa que describiría mejor esta experiencia?

¿Qué significa para usted SENSACIÓN DE ARDOR según se usó en esta afirmación? ¿Existe otra palabra o frase que piensa que describiría mejor esta experiencia?

¿Qué significa para usted LA CAPACIDAD FÍSICA PARA MOVILIZARSE en esta afirmación? ¿Existe otra palabra o frase que piensa que describiría mejor esta experiencia? Si tuviera que elegir entre “moverse” o “movilizarse”, ¿cuál palabra elegiría?

¿Qué significa para usted TENER PROBLEMAS PARA SENTARSE en esta afirmación? ¿Existe otra palabra o frase que piensa que describiría mejor esta experiencia? ¿Preferiría que se usara la frase “dificultad para sentarse”?

¿Qué significa para usted TAREAS DE LA CASA DIARIAS (LIMPIAR, COCINAR, HACER LA COLADA, LLEVAR LA CASA) según se usó en esta afirmación? ¿Hay otros ejemplos que piensa que funcionarían mejor para describir esta experiencia?

¿Qué significa para usted PROBLEMAS PERSONALES DIARIOS (BAÑÁNDOSE, VISTIÉNDOSE, AFEITÁNDOSE, ETC.) según se usó en esta afirmación? ¿Hay otros ejemplos que piensa que funcionarían mejor para describir esta experiencia?

¿Qué significa para usted PROBLEMAS PARTICIPANDO EN ACTIVIDADES DE OCIO (MIRANDO TELEVISIÓN, RELAJÁNDOSE) según se usó en esta afirmación? ¿Le plantea alguna dificultad la palabra “ocio”? ¿Preferiría que se utilice la frase “actividades que realiza en su tiempo libre”? ¿Hay otros ejemplos que piensa que funcionarían mejor para describir esta experiencia?

¿Qué significa para usted PROBLEMAS PARTICIPANDO EN ACTIVIDADES SOCIALES (SALIR A COMER, VISITAR AMIGOS) según se usó en esta afirmación? ¿Hay otros ejemplos que piensa que funcionarían mejor para describir esta experiencia?

¿Piensa que es importante preguntar sobre ACTIVIDADES DE OCIO y ACTIVIDADES SOCIALES? Si se le preguntara tan solo una de ellas, ¿cuál seleccionaría? ¿Por qué?

¿Qué significa para usted PROBLEMAS CON LA PRODUCTIVIDAD EN EL TRABAJO según se usó en esta afirmación? (PREGUNTE SI EL PARTICIPANTE NO ESTÁ TRABAJANDO) ¿Hay alguna otra palabra o frase que usted cree que describiría mejor esta experiencia?

¿Qué significa para usted DIFICULTAD CONCENTRÁNDOSE según se usó en esta afirmación?

¿Qué significa para usted DISMINUCIÓN DE PLACER DE LA ACTIVIDAD SEXUAL ANAL según se usó en esta afirmación?

¿Preferiría que se utilice la frase “placer físico” en vez de “placer” al preguntar sobre esta experiencia?

¿En qué se diferencia de DISMINUCIÓN DE PLACER POR OTRAS FORMAS DE ACTIVIDAD SEXUAL? ¿Piensa que es necesario que se le pregunte sobre ambos conceptos? Si se le preguntara tan solo uno de ellos, ¿cuál seleccionaría? ¿Por qué?

¿Qué significa para usted DISMINUCIÓN DE DESEO POR ACTIVIDAD SEXUAL ANAL según se usó en esta afirmación?

¿En qué se diferencia de DISMINUCIÓN DE DESEO POR OTRAS FORMAS DE ACTIVIDAD SEXUAL? ¿Piensa que es necesario que se le pregunte sobre ambos conceptos? Si se le preguntara tan solo uno de ellos, ¿cuál seleccionaría? ¿Por qué?

¿Qué significa para usted ESTOY PREOCUPADO QUE MI ENFERMEDAD EMPEORE según se usó en esta pregunta?

¿Qué significa para usted RELACIONES ÍNTIMAS según se usó en esta pregunta?

¿Preferiría que preguntásemos sobre la “intimidad afectiva con otras personas” en vez de “relaciones íntimas”?

Sondeo de la entrevista cognitiva – Comprensión de la escala de respuesta

En general, ¿qué tan difícil fue seleccionar respuestas para las afirmaciones que le pedían que seleccionara, para nada, un poco, algo, bastante, mucho? (DE EJEMPLOS DEL CUESTIONARIO)

- PARA NADA difícil
- UN POCO difícil
- ALGO difícil
- MUY difícil

Para lo siguiente debe encontrar un ítem para el que el paciente contestó con un 2 y determinar de qué manera difirió de una respuesta 1 o 3. También debe encontrar un ítem para el que el paciente contestó con un 3 y determinar de qué manera difirió de una respuesta 2 o 4.

Usted contestó (2). ¿Cómo llegó a esa respuesta? ¿Por qué es una mejor respuesta que (x+1)? ¿Por qué (x) es una mejor respuesta que (x-1)?

Usted contestó (3). ¿Cómo llegó a esa respuesta? ¿Por qué es una mejor respuesta que (x+1)? ¿Por qué (x) es una mejor respuesta que (x-1)?

¿Hubo algunas otras palabras en las opciones de respuesta que eran confusas o difíciles de entender? Si sí, ¿cuáles?

Sondeo de la entrevista cognitiva – Período recordatorio

¿Qué tan fácil o difícil fue pensar en sus experiencias en los últimos 7 días? ¿Existe un mejor período de tiempo para considerar sus experiencias?

Respuestas de resumen

Ahora que ha respondido todo, me gustaría hacerle un par de preguntas finales sobre la entrevista en su totalidad. Recuerde que tan solo nos interesa mejorar la encuesta, por lo que si algo le resultó confuso o difícil de contestar asegúrese de decirlo—eso es exactamente lo que queremos averiguar.

- *¿Le pareció difícil esta entrevista?*
- *¿Le pareció que la entrevista fue demasiado larga?*
- *¿Alguna afirmación en la encuesta sobresalió por ser particularmente difícil para usted?*
- *¿Hay algo más que le gustaría que supiéramos sobre este cuestionario? ¿Tiene alguna sugerencia para mejorarlo para otras personas?*

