This study adds a seventh phase to the development paradigm conducted with protocol AMC-A02, which will use the translated aHRSI in Spanish to complete cognitive interviews of Spanish-speaking participants. We will be conducting cognitive interviews (see Appendices [VI](#) and [VII](#)) of the finalized measure in Spanish (see Appendices [XI](#) and [XII](#)) to establish the content validity of the measure in Spanish. In addition to the cognitive interviews, we will collect a brief demographic form, and collect information on the participants preferred language and language proficiency (see Appendices [IX](#), [X](#), [XIII](#), and [XIV](#)) for each participant. We will enroll up to 40 eligible HIV-positive participants from participating ANCHOR sites using the same eligibility criteria as AMC-A02 phase 2 (except the age limit is lowered to 18 and the added criteria that Spanish be their first language as per self-report) over three rounds of cognitive interviewing, as was done for the English language version in AMC-A02 phases 4-6.¹⁸

- Cognitive Interviews in Spanish (Round 1): The process for conducting the cognitive interviews will be the same as for the English ones outlined above in Phase 4. We will plan to consent 20 Spanish speaking participants in order to complete 20 cognitive interviews.
- Cognitive Interviews in Spanish (Round 2): We will complete Phase 5 in Spanish in the exact same method as we did for the English version if it is necessary. If necessary, we will recruit up to 10 participants for this Phase 5 round.
- Cognitive Interviews in Spanish (Round 3): We will complete Phase 6 in Spanish in the exact same method as we did for the English version if it is necessary. If necessary, we will recruit up to 10 participants for this Phase 5 round.

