APPENDIX VII: COGNITIVE INTERVIEW SCRIPT – ENGLISH

Introduction (Read to Participant)

- *It is important to understand the experiences of people who are diagnosed with Anal HSIL (pre-cancer lesion in the anus) (and any treatments they receive – IF APPLICABLE). That is why we are asking for your help today. We would like you to answer some questions for the next hour. We will be asking you to use some of the new questions we are developing, and then to tell us your experiences answering these questions, such as how easy or difficult the questions were to answer. Some of these questions will ask you about your symptoms related to Anal HSIL (and treatment – IF APPLICABLE). Some questions will ask about how Anal HSIL (and treatment – IF APPLICABLE) has impacted parts of your everyday life. With your help, we will be able to have a better understanding of what people who have Anal HSIL are experiencing.*
- *The information that you provide today will be used for research purposes, and will help people in the future.*

ANCHOR ANAL HSIL HEALTH-RELATED QUALITY OF LIFE INDEX---DRAFT 2015v.7

Below is a list of statements that other people diagnosed with anal HSIL (pre-cancer lesion in the anus) and treated or actively monitored have said are important. Please check the box to select your answer based on your experiences in the past 7 days. If you have **ANY** trouble selecting a response for any statement or find something hard to understand, please check the box in the *Check if Difficult to Understand* column for that statement. Please let me know when you have completed each of the three sections (Physical Symptoms, Physical Impacts, Psychological Symptoms).

PHYSICAL SYMPTOMS		Check if Not Applicable	Not at all 0	A little bit 1	Somewhat 2	Quite a bit 3	Very much 4	Difficult To Understand
1. I have anal pain								
2. I have pain other than anal pain								
3. I have pain during bowel movements								
4. I have constipation								
5. I have bleeding from the anus								
6. I have itching in or around the anus								
7. I have discharge (wetness) in my anal area								
8. I have burning sensations in the anal area								
9. I have urgency for bowel movements								
PHYSICAL IMPACTS		Check if Not Applicable	Not at all 0	A little bit 1	Somewhat 2	Quite a bit 3	Very much 4	Difficult To Understand
10. I have problems with my physical ability to move around								
11. I have problems with sitting								

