12. I have problems completing daily household chores (e.g., cleaning, cooking, laundry, house maintenance)								
13. I have problems taking care of myself (e.g., bathing, dressing, shaving)								

14. I have problems participating in leisure activities (e.g., watching television, relaxing)							
15. I have problems participating in social activities (e.g., going out to eat, visiting friends)							
16. I have problems with work productivity							
PSYCHOLOGICAL SYMPTOMS	Check if Not Applicable	Not at all 0	A little bit 1	Somewhat 2	Quite a bit 3	Very much 4	Difficult To Understand
17. I have difficulty concentrating							
18. I have a decreased enjoyment of anal sexual activity							
19. I have a decreased enjoyment for any form of sexual activity other than anal sexual activity							
20. I have a decreased desire for anal sexual activity							
21. I have decreased desire for forms of sexual activity other than anal sexual activity							
22. I am worried about my condition getting worse							
23. I have anxiety							
24. I have depression							
25. I have problems with my intimate relationships							

Now let's quickly go through and have you tell me what your responses were to each of the 25 items [RECORD RESPONSES ON YOUR FORM]. Please let me know if you checked off 'Difficult to Understand' or 'Not Applicable' for any of the items.

Cognitive Interviewing Probes – General

First, for the statements that you responded to, was it easy to answer....

- All of the time
- Most of the time
- Some of the time
- None of the time

Were there any problems that made it difficult for you to answer the survey in general? If so, what were they?

Now let's go back and discuss any of those areas where you indicated that the statement was hard to understand. Putting aside issues that you have already told me about, what were the issues or problems that came up for you in those places?

(Some of the issues raised during this portion may probe specific issues that we are targeting, please make note of these to work toward not repeating these issues again in the interview)

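### The Spanish instruction for the 'Difícil de entender' tick box asks about difficulty answering, not understanding, so some comprehension problems may go unflagged, mainly on five items that have no probe of their own.

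*Protocol*

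**What the plan says.** Sections 2.3 and 4.0 give the purpose of the Spanish cognitive interviews as "to establish the content validity of the measure in Spanish". Section 2.3 adds that Round 1 follows the same process as the English interviews.

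In both scripts the participant completes a 25-item form with a last column for items that are difficult to understand, and an introductory sentence says when to tick it. In Appendix VII the participant ticks on having any "trouble selecting a response for any statement or find something hard to understand, please check the box in the" named column. In Appendix VIII the participant ticks on having any "problema seleccionando una respuesta o le cuesta contestar algo, por favor seleccione la casilla en la columna que dice" "Difícil de entender". The stand-alone Spanish form in Appendix XII has the same column but no sentence explaining it, so the sentence in Appendix VIII is the only Spanish instruction for the flag.

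The interviewer then has the participant read back the answers and say which items were ticked, and records this. An open discussion follows. It begins "Now let's go back and discuss any of those areas where you indicated that the statement was hard to understand" in English and "Ahora examinemos lo que le pareció difícil de entender" in Spanish. Item-specific probes, questions on the response scale and recall period, and closing questions come after it.

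**The concern.** The English sentence gives two different reasons to tick: difficulty choosing a response and difficulty understanding. The Spanish sentence gives difficulty choosing a response and difficulty answering, which are nearly the same thing. *Contestar* is to answer. *Entender*, to understand, appears only in the column heading to which the sentence points.

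The participant who matters most for a translation is the one who reads an item with doubt, or in an unintended sense, and still gives an answer. The English sentence asks that person to tick if the doubt is noticed. The Spanish sentence does not ask for it explicitly. A missed flag would also be hard to recover, because Sections 3.4.2 and 7.1 provide for deletion of the recordings within 48 business hours and for no transcripts. After that only the recorded responses, notes and summaries remain.

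**Working it through.** The protocol states no figure on this point, so there is none to reproduce. The check sets the two scripts side by side and then counts the items for which the tick matters most.

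**1. The triggers compared**

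| | Appendix VII (English) | Appendix VIII (Spanish) |
|---|---|---|
| First trigger | trouble selecting a response | trouble selecting a response |
| Second trigger | something hard to understand | something hard to answer |
| Column named | difficult to understand | difficult to understand |

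Only the second trigger differs. The difference is one of meaning, not style.

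**2. Items with a probe that does not depend on a tick** (question-specific probes, Appendix VIII)

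- Items 1 to 3: one shared probe, on whether the types of pain are distinct rather than on what the wording means (3 items).
- Item 6: meaning probe (1).
- Item 7: probe on the preferred word, asked only if the participant has the symptom (1).
- Item 8: meaning probe, for example "Qué significa para usted SENSACIÓN DE ARDOR según se usó en esta afirmación" (1).
- Items 10 to 16: meaning probes (7).
- Items 17 to 22: meaning probes, with items 19 and 21 asked as a contrast with the item before (6).
- Item 25: meaning probe (1).

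Sum: 3 + 1 + 1 + 1 + 7 + 6 + 1 = 20. The remaining 25 − 20 = 5 items have no probe of their own in either language: 4 (constipation), 5 (bleeding), 9 (bowel urgency), 23 (anxiety) and 24 (depression).

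**3. Exposure**

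Section 3.3.1 gives 20 to 40 participants, each with one interview.

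- Items with no probe of their own: 5 × 20 = 100 to 5 × 40 = 200 item responses.
- Adding items 1 to 3 and 7, whose probes are partial: 9 × 20 = 180 to 9 × 40 = 360.
- All items: 25 × 20 = 500 to 25 × 40 = 1,000.

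These are counts of responses collected under the faulty instruction. None estimates how many flags would be missed, because the protocol gives no rate of comprehension problems and no rate of ticking under either wording.

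**The case against.** The best defence is that the tick is one safeguard among several.

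- The column heading still names comprehension, and the interviewer asks about that column by name when the answers are read back.
- The first Spanish trigger is emphasised and broad. Someone who guesses because the wording is unclear may well regard that as a problem selecting a response.
- The Spanish follow-up, "Ahora examinemos lo que le pareció difícil de entender", asks what seemed hard to understand. Unlike the English line, it does not refer to what the participant indicated, so an unticked item can be raised.
- Later questions ask about confusing words in the answer options and about any particularly difficult statement, and they reach all items.
- Section 5.0 has an expert panel code the interviews, and no rule in the protocol uses tick counts.

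All of this stands, and it limits the point. A reader might infer that comprehension problems in participants who can answer will go unflagged, or that the ticks alone decide what is discussed. The documents support neither.

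A reader might also blame the Spanish wording for ticks by participants who understand an item, such as a sexual one, but find it awkward to answer. The English invites these too, through trouble selecting a response, so they are not peculiar to the translation.

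The defence does not remove the mismatch. The backstops are general, and for the five items they depend on the participant recalling and volunteering a difficulty. The probe on the instructions will not expose the fault either, because the passage it re-reads omits the tick-box sentence.

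**Conclusion.** The point holds as a translation error in an operative instruction. Appendix VIII has no explicit comprehension trigger, departs from Appendix VII and disagrees with its own column heading. Comprehension problems in participants who can still answer may go unflagged. The risk is mainly for items 4, 5, 9, 23 and 24, where the tick is the only scripted prompt tied to the individual item whatever answer is given: 100 to 200 item responses exposed.

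It would be tempting to give the size as all 500 to 1,000 item responses. That would treat the tick as the only safeguard, whereas 20 of the 25 items have a probe regardless of ticking, though a partial one for items 1 to 3 and 7.

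The conclusion assumes that interviewers read the scripts as printed and that enrolment stays between 20 and 40. The point is worth correcting because comprehension in Spanish is what the study sets out to examine. It does not threaten the study as a whole.

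**What to change.** In the tick-box sentence of Appendix VIII, replace the verb *contestar* with *entender*, so that the clause reads *le cuesta entender algo*. Instruction, column heading and follow-up question then agree, and the Spanish matches Appendix VII.

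The protocol does not show whether Round 1 has begun, so the change should apply before the next interview. If some interviews have already used the present wording, record from which interview the corrected wording applies.

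The change is one word but not free. Section 7.2 requires a written amendment for any change, approved by the Protocol Chair and by the IRB of each participating institution. It adds no interview time and no participants. It does not address ticks from participants who understand an item but struggle to choose an answer, because that trigger stays in both languages.
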